8.2 Safety assessments

Planned time points for all safety assessments are provided in the SoA.

8.2.1 Physical examinations

Full and targeted physical examinations will be performed according to the assessment schedules (see the SoAs) and in unscheduled visits. Full physical examinations will include assessments of the head, eyes, ears, nose, and throat and the respiratory, cardiovascular, GI, urogenital, musculoskeletal, neurological, dermatological, hematologic/lymphatic, and endocrine systems. Height and weight will be measured at screening, and q4w (on dosing days only). Targeted physical examinations are to be utilized by the Investigator on the basis of clinical observations and symptomatology. Situations in which physical examination results should be reported as AEs are described in Section 8.3.7.

8.2.2 Clinical safety laboratory assessments

Blood and urine samples for determination of clinical chemistry, hematology, and urinalysis will be taken at the times indicated in the assessment schedules and as clinically indicated (see the SoAs).

Clinical laboratory safety tests, including serum pregnancy tests, will be performed in a licensed clinical laboratory according to local standard procedures. Sample tubes and sample sizes may vary depending on the laboratory method used and routine practice at the site. Pregnancy tests (performed only on female patients of childbearing potential) may be performed at the site using a licensed test (urine or serum pregnancy test). Abnormal clinically significant laboratory results should be repeated as soon as possible (preferably within 24 to 48 hours).

Additional safety samples may be collected if clinically indicated at the discretion of the Investigator. The date, time of collection, and results (values, units, and reference ranges) will be recorded on the appropriate CRF.

The laboratory variables to be measured are presented in Table 19 (clinical chemistry), Table 20 (hematology), and Table 21 (urinalysis).

Other safety tests to be performed at screening include assessment for hepatitis B surface antigen, hepatitis C antibodies, and HIV antibodies.

The following laboratory variables will be measured:

Table 19 Clinical chemistry

Albumin	Lipase ^b
Alkaline phosphatase	Magnesium ^c
ALT ^a	Potassium
Amylase ^b	Sodium
AST ^a	Total bilirubin ^a
Bicarbonate ^c	Total protein
Calcium	TSH ^e
Chloride ^c	T3 free ^f (reflex)
Creatinine ^d	T4 free ^f (reflex)
Gamma glutamyltransferase ^e	Urea or blood urea nitrogen, depending on local practice
Glucose	
Lactate dehydrogenase	

^a Tests for ALT, AST, alkaline phosphatase, and TBL must be conducted and assessed concurrently. If TBL is $\geq 2 \times$ upper limit of normal (and no evidence of Gilbert's syndrome), then fractionate into direct and indirect bilirubin.

^b It is preferable that both amylase and lipase parameters are assessed. For sites where only 1 of these parameters is routinely measured, either lipase or amylase is acceptable.

^c Bicarbonate (where available), chloride, creatinine clearance, gamma glutamyltransferase, magnesium testing are to be performed at baseline, on Day 1 (unless all screening laboratory clinical chemistry assessments are performed within 3 days prior to Day 1), and if clinically indicated.

^d Creatinine clearance will be calculated by data management using the Schwartz pediatric equation, radioisotope measured GFR, or by 24-hour urine collection.

^e If TSH is measured within 14 days prior to Day 1 (first infusion day), it does not need to be repeated at Day 1. TSH will be collected every 4 weeks.

^f Free T4 or free T3 will only be measured if TSH is abnormal or if there is a clinical suspicion of an AE related to the endocrine system. Free T4 can be collected with or without free T3.

AE Adverse event; ALT Alanine aminotransferase; AST Aspartate aminotransferase; GFR glomerular filtration rate; T3 Triiodothyronine; T4 Thyroxine; TBL total bilirubin; TSH Thyroid-stimulating hormone.

Table 20 Hematology

Absolute neutrophil count ^a	Absolute lymphocyte count ^a
Hemoglobin	Platelet count
Total white cell count	
Coagulation ^b	

^a Can be recorded as absolute counts or as percentages. Absolute counts will be calculated by Data Management if entered as percentage. Total white cell count therefore has to be provided.

^b For coagulation parameters, activated partial thromboplastin time and international normalized ratio are to be assessed at baseline on Day 1 (unless all screening laboratory hematology assessments are performed within 3 days prior to Day 1), and as clinically indicated.

Table 21 Urinalysis

Bilirubin	Ketones
Blood	pH
Color and appearance	Protein
Glucose	Specific gravity

Note: Urinalysis should be done at the visits shown in [Table 1](#) (for dose-finding) and [Table 2](#) (for dose-expansion).

Note: Microscopy should be used as appropriate to investigate white blood cells and use the high power field for red and white blood cells.

Results for LFTs, electrolytes, full blood count, urea, and creatinine must be available before commencing an infusion (within 3 days) and reviewed by the treating physician or Investigator prior to dosing.

If a patient shows an AST or ALT $\geq 3 \times$ ULN together with TBL $\geq 2 \times$ ULN, refer to [Appendix D](#) for further instructions on cases of increases in liver biochemistry and evaluation of Hy's Law. These cases should be reported as SAEs if, after evaluation, they meet the criteria for a Hy's law case or if any of the individual liver test parameters fulfill any of the SAE criteria.

All patients should have further chemistry profiles performed at 30 days (± 3 days) after permanent discontinuation of IP (see [Table 3](#)).

Any clinically significant abnormal laboratory values should be repeated as clinically indicated and recorded on the CRF. Situations in which laboratory safety results should be reported as AEs are described in [Section 8.3.7](#).

All patients with Grade 3 or 4 laboratory values at the time of completion or discontinuation from IP must have further tests performed until the laboratory values have returned to Grade 1 or 2, unless these values are not likely to improve because of the underlying disease.

8.2.3 Vital signs

Vital signs (blood pressure [BP], pulse, temperature, and respiration rate) will be evaluated according to the SoAs. Peripheral oxygen saturation will be measured at screening/baseline and at clinic visits, in accordance with the SoA, along with the remaining vital signs.

Patients will be monitored and vital signs collected/recorded in CRF as presented in the bulleted list below:

- Based on a 120-minute infusion (durvalumab):
 - Prior to the beginning of the infusion (measured once from approximately 30 minutes before up to 0 minutes [ie, the beginning of the infusion])
 - Approximately 60 minutes during the infusion (**halfway** through infusion)
 - At the end of the infusion (approximately 120 minutes \pm 5 minutes).
- Based on a 60-minute infusion (durvalumab and tremelimumab):
 - Prior to the beginning of the infusion (measured once from approximately 30 minutes before up to 0 minutes [ie, the beginning of the infusion])
 - Approximately 30 minutes during the infusion (**halfway** through infusion)
 - At the end of the infusion (approximately 60 minutes \pm 5 minutes).

If the infusion takes longer than 60 minutes then BP and pulse measurements should follow the principles as described above or be taken more frequently if clinically indicated.

Dose-finding phase

Vital signs will be obtained and documented prior to, mid-infusion, and end of infusion for the following:

- Cycle 1 Day 1: Durvalumab infusion.
- Cycle 2 Day 1: Tremelimumab and durvalumab infusion.

For Cycle 3 onwards, only at the beginning of the first infusion:

- Patients should be carefully monitored, and BP and other vital signs should be measured during and post infusion as per institution standard, and as clinically indicated. Any clinically significant changes in vital signs should be entered onto an unscheduled vital signs CRF page.

For the observation period:

- Cycle 1 Day 1 : 1 hour after completion of durvalumab infusion.
- Cycle 2 Day 1 to Cycle 4 Day 1: 1 hour between tremelimumab and durvalumab.
- Cycle 2 Day 1: 1 hour after completion of tremelimumab and durvalumab infusions.

Dose-expansion phase

Vital signs will be obtained and documented prior to, mid-infusion and end of infusion for the following:

- Cycle 1 Day 1: Tremelimumab and durvalumab infusion.

For Cycle 2 onwards, only at the beginning of first infusion:

- Patients should be carefully monitored, and BP and other vital signs should be measured during and post infusion as per institution standard, and as clinically indicated. Any clinically significant changes in vital signs should be entered onto an unscheduled vital signs CRF page.

For the observation period:

- Cycle 1 Day 1: 1 hour between tremelimumab and durvalumab;
 - For Cycle 2 onwards: if no infusion reaction, observation period may be waived allowing durvalumab to be administered immediately after tremelimumab.
- Cycle 2 Day 1: 1 hour after completion of tremelimumab and durvalumab infusions.

Situations in which vital signs results should be reported as AEs are described in Section 8.3.7. For any AEs of infusion reactions, the vital signs values should be entered into the CRF.

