8.3.7 Adverse events based on examinations and tests

The results from the Clinical Study Protocol mandated laboratory tests and vital signs will be summarized in the clinical study report (CSR). Deterioration as compared to baseline in protocol mandated laboratory values, vital signs, physical examination findings, or ECG should therefore only be reported as AEs if they fulfill any of the SAE criteria or are the reason for discontinuation of treatment with the IP.

If deterioration in a laboratory value/vital sign is associated with clinical signs and symptoms, the sign or symptom will be reported as an AE and the associated laboratory result/vital sign will be considered as additional information. Wherever possible, the reporting Investigator uses the clinical, rather than the laboratory term (eg, anemia versus low hemoglobin value). In the

absence of clinical signs or symptoms, clinically relevant deteriorations in non-mandated parameters should be reported as AE(s).

Deterioration of a laboratory value, which is unequivocally due to PD, should not be reported as an AE/SAE.

Any new or aggravated clinically relevant abnormal medical finding at a physical examination as compared with the baseline assessment will be reported as an AE unless unequivocally related to the disease under study, see Sections 8.3.9 and 8.3.10.

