4.1.3 Time Windows

Safety assessments

Time windows will need defining for any presentations that summarize values by visit. The following conventions apply:

- The time windows should be exhaustive so that data recorded at any time point has the potential to be summarized. Inclusion within the time window should be based on the actual date and not the intended date of the visit.
- All unscheduled visit data should have the potential to be included in the summaries.
- The window for the visits following baseline will be constructed in such a way that the upper limit of the interval falls halfway between the two visits (the lower limit of the first post-baseline visit will be Day 2). If an even number of days exists between two consecutive visits, then the upper limit will be taken as the midpoint value minus 1 day. For example, the visit windows for vital signs data in the dose-expansion phase for patients' treatment with durvalumab in combination with tremelimumab are:
 - Cycle 1 Day 8 visit window day 2-11
 - Cycle 1 Day 15 visit window day 12 - 21
 - Cycle 2 Day 1 visit window day 22 - 35
 - Cycle 2 Day 15 visit window day 36 - 49
 - Cycle 3 Day 1 visit window day 50 – 63
 - etc
- The upper limit for the last record on treatment will consider end of treatment date and not date of disease progression.
- For summaries showing the maximum or minimum values, the maximum/minimum value recorded on treatment will be used (regardless of where it falls in an interval).
- Listings should display all values contributing to a time point for a patient.
- For visit based summaries:
 - If there is more than one value per patient within a time window then the closest value to the scheduled visit date should be used, or the earlier in the event the values are equidistant from the nominal visit date. The listings should highlight the value for that patient that went into the summary table, wherever feasible. Note: in summaries of extreme values all on-treatment values collected are used including those collected at unscheduled visits.
 - To prevent very large tables or plots being produced that contain many cells with meaningless data for outputs in the dose expansion phase, for each treatment group visit data should only be summarized if the number of observations is greater than the minimum of 5 of patients dosed.

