4.2.3.4 Vital signs

Height, weight, BMI, Pulse rate, respiratory rate, systolic and diastolic blood pressure, peripheral oxygen saturation and temperature will be listed by patient and summarized for the absolute value at each visit.

Box plots for absolute values and change from baseline by visit may be presented for certain vital signs parameters if warranted after data review.

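### As written, SAP 4.1.3 and 4.2.3.4 leave the mid- and end-of-infusion vital signs required by Protocol 8.2.3 out of every planned vital-sign summary

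*Protocol*

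**What the plan says.** **Collection.** Protocol 8.2.3 states: "Vital signs will be obtained and documented prior to, mid-infusion, and end of infusion for the following". For dose-finding it lists the durvalumab infusion on Cycle 1 Day 1 and "Cycle 2 Day 1: Tremelimumab and durvalumab infusion". For dose-expansion it lists "Cycle 1 Day 1: Tremelimumab and durvalumab infusion". In later cycles the routine reading is taken before the first infusion only, and clinically significant changes go on an unscheduled vital-signs page.

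**Baseline and windows.** SAP 4.1.2 treats anything recorded after the first dose as post-baseline. SAP 3.3 counts vital signs as on-treatment from the date of first treatment. SAP 4.1.3 asks for exhaustive windows, but also says that "the lower limit of the first post-baseline visit will be Day 2". Its worked example, which is for dose-expansion vital signs, opens with "Cycle 1 Day 8 visit window day 2-11". When a window holds several values for one patient, "then the closest value to the scheduled visit date should be used, or the earlier in the event the values are equidistant".

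**Outputs.** Under SAP 4.2.3.4 vital signs "will be listed by patient and summarized for the absolute value at each visit". By-visit box plots are optional. The SAP amendment history records that the vital-sign shift and change-from-baseline tables were removed.

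**AE reporting.** Protocol 8.3.7 begins: "The results from the Clinical Study Protocol mandated laboratory tests and vital signs will be summarized in the clinical study report". On that ground it limits AE reporting of a vital-sign deterioration to one that meets SAE criteria or leads to discontinuation. If there are signs or symptoms, the sign or symptom is reported as the AE.

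**The concern.** The protocol asks sites to measure children during and at the end of the first infusions, and the SAP then has no planned summary in which those measurements can appear. Two written rules cause this, not silence: the Day 2 start and the earlier-value tie-break. The first also conflicts with the SAP's own requirement that windows be exhaustive.

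The link to Protocol 8.3.7 makes this more than a layout question. The protocol narrows AE reporting because it expects the CSR to summarize vital signs. For infusion-time readings that summary is not planned, so an asymptomatic, non-serious fall or rise that does not stop treatment would appear in neither an AE table nor a vital-sign table.

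Vital signs are a named endpoint of a primary dose-finding objective and of the dose-expansion safety objective. Protocol 4.3.1.1 says the combination has not been studied in children. A CSR reader could take unremarkable infusion-day rows as evidence of stability during infusion when they hold only pre-infusion values.

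**Working it through.** **1. The SAP's own windows.** The rule in SAP 4.1.3 is: first lower limit Day 2; upper limit at the midpoint between consecutive nominal visits; one day less when the midpoint is a whole day. For dose-expansion visits on days 8, 15, 29, 43 and 57:

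- (8 + 15)/2 = 11.5, so the first window is 2–11
- (15 + 29)/2 = 22, less 1 = 21, giving 12–21
- (29 + 43)/2 = 36, less 1 = 35, giving 22–35
- (43 + 57)/2 = 50, less 1 = 49, giving 36–49

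These four match the SAP. The fifth printed window, 50–63, does not: the next visit is Cycle 4 Day 1 (day 85), and (57 + 85)/2 = 71, less 1 = 70. That is a separate slip with no bearing here.

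Dose-finding adds Cycle 2 Day 8 (day 36). Since (29 + 36)/2 = 32.5, the Cycle 2 Day 1 window is 22–32.

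**2. Cycle 1 Day 1.** All readings fall on study day 1. Those taken before the first dose can serve as baseline. Later ones are post-baseline, and the earliest window opens on day 2. Selected from mid- and end-of-infusion readings: 0 in either phase.

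**3. Cycle 2 Day 1, dose-finding.** All six readings share one date, nominally day 29. They are equally far from the nominal date, so the earlier rule picks the first, the pre-tremelimumab reading.

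The rule was also run with Cycle 2 Day 1 moved from 4 days early to 14 days late, with the Day 8 and Day 15 visits moving with it. A mid- or end-of-infusion reading was chosen in none of the 19 cases. At 4 days early, the reading from the following visit (day 32) is closer to day 29 than the dosing-day readings (day 25) and is used instead. With 4 to 14 days' delay, the pre-tremelimumab reading is taken into a later visit's window. The one exception found: if the pre-tremelimumab reading is missing, the mid-tremelimumab reading is selected.

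**4. Count per patient, nominal schedule.**

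| Phase | Required sets | Used | Not in any by-visit summary | Of which mid/end |
|---|---|---|---|---|
| Dose-finding | 3 (C1D1) + 6 (C2D1) = 9 | 2 (baseline; C2D1 pre-tremelimumab) | 7/9 = 78% | 6 of 6 |
| Dose-expansion | 6 (C1D1) | 1 (baseline) | 5/6 = 83% | 4 of 4 |

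The one further unused set in each phase is the pre-durvalumab reading taken after tremelimumab.

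**5. Other routes into a summary.** The maximum/minimum convention in SAP 4.1.3 uses all on-treatment values, but SAP 4.2.3.4 plans no such vital-sign output. SAP 3.3.4 still calculates change from baseline to each scheduled visit, but no table is planned for it, and it is by visit. The optional box plots are also by visit. None of these brings the readings back.

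**6. Later cycles.** An unscheduled infusion-time value shares its date with the routine pre-infusion value, so the same tie-break can pass over it even when it is clinically significant.

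**The case against.** The strongest reply is that little is hidden. SAP 4.1 and 4.2.3.4 list all data by patient. Dose-finding plans a minimum of 12 and a maximum of 45 patients, and dose-expansion at most 36 evaluable, so listings can be read. Symptomatic deteriorations are AEs under Protocol 8.3.7. Infusion-related and hypersensitivity reactions are AESIs, which SAP 4.2.3.2 tabulates by grade, outcome and dose interruption or discontinuation. The Data Review Committee works from the clinical database, and no decision rule in the documents depends on the by-visit vital-sign table. The sponsor deliberately dropped the shift and change tables, and the mock shells, which are not in the documents, may split infusion days by time point.

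Most of this stands and limits the point. It does not remove it. A listing is not the summary on which Protocol 8.3.7 relies, and the changes at issue are the ones that section keeps out of AE reporting. Removing two by-visit tables says nothing about infusion time points, and shells that split by time point would depart from the SAP's written rules. Reading the tie-break as referring to an earlier date only would not help either: the SAP would then have no rule for same-day readings.

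Stronger readings are tempting but unsupported:

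- A reader might infer that the tables hold only pre-infusion readings. They do not: Cycle 1 Days 8 and 15, Cycle 2 Day 8 (dose-finding), Cycle 2 Day 15 and End of Treatment readings are scheduled, and non-dosing-day visits have windows.
- A reader might infer that most infusion-time changes reach no AE table. The documents give no share.
- A reader might extend the point to oxygen saturation. Protocol 8.2.3 lists blood pressure, pulse, temperature and respiration rate as vital signs and ties saturation to screening and clinic visits. The schedule of activities puts it in the vital-signs row, so a mid-infusion saturation reading is not clearly required.

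**Conclusion.** The point holds in limited form. Under the SAP as written, the mid- and end-of-infusion readings required on Cycle 1 Day 1 (both phases) and Cycle 2 Day 1 (dose-finding) enter no planned vital-sign summary, apart from the missing-value exception on Cycle 2 Day 1. Per patient that is all 6 such reading sets in dose-finding and all 4 in dose-expansion. Counting the second pre-infusion set as well, it is 7 of 9 and 5 of 6.

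These fractions count readings left unsummarized. They do not measure data lost or safety events missed. The practical gap is asymptomatic, non-serious infusion-time change, chiefly in blood pressure, pulse, temperature and respiration rate, that does not stop treatment.

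The conclusion assumes that same-day readings are equidistant from the nominal date, that the Cycle 1 Day 1 pre-infusion reading is the baseline and is shown in the tables, and that the shells follow the SAP text. The counts are for the nominal schedule; shifting Cycle 2 Day 1 can change which other reading is used, but selected no mid- or end-of-infusion reading in any case checked.

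**What to change.** In SAP 4.1.3, exempt infusion-day vital signs from the Day 2 window start and from the earlier-value rule.

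In SAP 4.2.3.4:

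- Summarize Cycle 1 Day 1 (both phases) and Cycle 2 Day 1 (dose-finding) by nominal time point: pre, mid and end, for each infusion. Show the absolute value and the change from that infusion's own pre-infusion reading.
- Add a per-patient worst on-treatment value (maximum and minimum) that includes unscheduled readings. SAP 4.1.3 already has the convention for it.

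The cost is SAP wording and one or two extra tables. The data are already collected, and no visit, assessment or site instruction changes.

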^f Results for LFTs, electrolytes, full blood count, urea, and creatinine must be available before commencing an infusion (within 3 days) and reviewed by the treating physician or Investigator prior to dosing. If screening clinical chemistry and hematology assessments are performed within 3 days prior to Day 1 (first infusion day), they do not need to be repeated at Day 1. For coagulation parameters, activated partial thromboplastin time and international normalized ratio are to be assessed at baseline on Day 1 (unless performed within 3 days prior to Day 1).

^g If TSH is measured within 14 days prior to Day 1 (first infusion day), it does not need to be repeated at Day 1. TSH to be measured every 4 weeks from baseline.

^h Free T4 ± free T3 will only be measured if TSH is abnormal or if there is clinical suspicion of an AE related to the endocrine system.

ⁱ For females of childbearing potential only. A urine or serum pregnancy test is acceptable. Females of childbearing potential are required to have a pregnancy test within 7 days prior to the first dose of IP and then every 4 weeks. Pregnancy test may occur on Day 1, but results must be available and reviewed by the treating physician or Investigator prior to commencing an infusion.

^j Predose within 60 minutes of start of the 1st infusion.

^k Within 10 minutes of the end of the 2nd infusion.

- ¹ During the combination treatment period, predose samples for durvalumab PK samples should ideally be taken in the window after tremelimumab has been infused and before durvalumab is infused, within 60 minutes of start of infusion. However, sampling prior to tremelimumab infusion is also acceptable, if considered necessary for logistical/operational reasons.
- ^m The C7 follow-up tremelimumab PK and ADA sample will be taken 3 months (± 1 week) after the last dose of this IP (Table 3).
- ⁿ Kamofsky scale to be used for patients ≥ 16 years of age; Lansky scale to be used for patients ≥ 1 and < 16 years of age.
- ^o For AEs/SAEs reported during screening, additional information such as medical history and concomitant medications may be needed.
- ^p During the combination portion of treatment, tremelimumab will be administered first; the durvalumab infusion will start approximately 1 hour after the end of the tremelimumab infusion. See Section 6.1.2 (Study Drug Administration).

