All screening evaluations must be completed and reviewed to confirm that potential patients meet all eligibility criteria. The screening procedures (presented in [Table 1](#) and [Table 2](#)) will be completed within 28 days of signing the ICF and before durvalumab infusion on Cycle 1 Day 1 (radiological assessments to be completed within 21 days before on Cycle 1 Day 1). The Investigator will maintain a screening log to record details of all patients screened and to confirm eligibility or record reasons for screening failure, as applicable. At screening, consenting patients are assessed to ensure that they meet eligibility criteria (Sections [5.1](#) and [5.2](#)). Patients who do not meet these criteria must not be started on treatment. Patients will be considered to be in the screening period until all screening visit assessments are completed and eligibility is confirmed. Patients will be considered to be in the dose-finding period after the first dose of durvalumab has been administered.

Dose-finding phase

Descriptions of the procedures for this period are included in the SoA for the dose-finding phase of the study (Table 1).

Patients will receive durvalumab monotherapy on Cycle 1 Day 1 and will be closely monitored for 28 days for safety and tolerability (DLT observational period 1) attending clinic visits on Days 8 and 15. Starting on Cycle 2, patients will receive durvalumab + tremelimumab in combination on Day 1 and attend clinic visits on Days 8 and 15. Cycle 2 Day 1 to Day 28 is the second DLT observational period; the total DLT observational period is 56 days or 2 cycles. Starting at Cycle 3, patients will have a scheduled visit only on Day 1 of the treatment cycle. From Cycle 6 onwards, patients will receive durvalumab monotherapy until progression.

Dose-expansion phase

Once a RP2D has been confirmed, patients will be recruited to the dose-expansion phase and will follow the procedures for this period in Table 2. All patients will receive durvalumab + tremelimumab in combination on Day 1 of Cycles 1, 2, 3, and 4. From Cycle 5, patients will receive durvalumab monotherapy until progression.

Off-treatment follow-up

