8.3.13 Adverse events of special interest

An AESI is one of scientific and medical interest specific to understanding of the IP and may require close monitoring. An AESI may be serious or non-serious. The rapid reporting of AESIs allows ongoing surveillance of these events in order to characterize and understand them in association with the use of this IP.

Adverse events of special interest for durvalumab ± tremelimumab include but are not limited to events with a potential inflammatory or immune-mediated mechanism and which may require more frequent monitoring and/or interventions such as steroids, immunosuppressants and/or hormone replacement therapy. These AESIs are being closely monitored in clinical studies with durvalumab monotherapy and combination therapy. An imAE is defined as an AESI that is associated with drug exposure and is consistent with an immune-mediated mechanism of action and where there is no clear alternate etiology. Serologic, immunologic, and histologic (biopsy) data, as appropriate, should be used to support an imAE diagnosis. Appropriate efforts should be made to rule out neoplastic, infectious, metabolic, toxin, or other etiologic causes of the imAE.

If the Investigator has any questions in regards to an event being an imAE, the Investigator should promptly contact the Study Physician.

AESIs observed with durvalumab ± tremelimumab include:

- Diarrhea/colitis and intestinal perforation
- Pneumonitis/ILD
- Endocrinopathies (ie, events of hypophysitis/hypopituitarism, adrenal insufficiency, hyper- and hypo-thyroidism and type I diabetes mellitus)
- Hepatitis/transaminase increases
- Nephritis/blood creatinine increases
- Pancreatitis/serum lipase and amylase increases

- Rash/dermatitis
- Myocarditis
- Myositis/polymyositis
- Neuropathy/neuromuscular toxicity (eg, Guillain-Barré, and myasthenia gravis)
- Other inflammatory responses that are rare/less frequent with a potential immune-mediated etiology include, but are not limited to, pericarditis, sarcoidosis, uveitis, and other events involving the eye, skin, hematological, neuromuscular toxicities (eg, Guillain-Barré syndrome, myasthenia gravis) and rheumatological events.

In addition, infusion-related reactions and hypersensitivity/anaphylactic reactions with a different underlying pharmacological etiology are also considered AESIs.

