With the above considerations, the sample size for evaluable patients in the dose-expansion phase is expected to range from 21 to 36. Assuming that about 20% of patients may not be evaluable for ORR, the total number of patients dosed in the dose-expansion phase may range from approximately 25 to 43.

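### In dose-expansion, the one-hour observation after the infusions is listed at Cycle 2 Day 1, although both drugs are first given on Cycle 1 Day 1

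*Protocol*

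**What the plan says.** Protocol Section 8 states the dose-expansion regimen: "All patients will receive durvalumab + tremelimumab in combination on Day 1 of Cycles 1, 2, 3, and 4". Section 6.1.1.2 agrees. The first exposure to each drug, and to the combination, is therefore Cycle 1 Day 1.

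Section 6.1.2 sends the reader to Section 8.2.3 for vital signs and observation periods. For dose-expansion, Section 8.2.3 specifies:

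- Vital signs before, midway through and at the end of infusion: "Cycle 1 Day 1: Tremelimumab and durvalumab infusion". From Cycle 2 they are required only at the start of the first infusion, with anything further left to institutional standard and clinical need.
- Observation between the drugs: "Cycle 1 Day 1: 1 hour between tremelimumab and durvalumab". From Cycle 2 this may be waived if there was no infusion reaction.
- Observation after the infusions: "Cycle 2 Day 1: 1 hour after completion of tremelimumab and durvalumab infusions". This is the only post-infusion entry for the phase.

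For dose-finding, the same section lists two post-infusion hours. One is at Cycle 1 Day 1, "1 hour after completion of durvalumab infusion". The other is at Cycle 2 Day 1, after both infusions, in the same words as the dose-expansion line.

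Table 2 adds no observation period in its visible rows. Footnote k sets the timing of the post-infusion PK sample: "Within 10 minutes of the end of the 2nd infusion".

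**The concern.** In dose-finding, the post-infusion hour follows first exposure: first to durvalumab at Cycle 1, then to the combination at Cycle 2. In dose-expansion first exposure moved to Cycle 1, but the hour stayed at Cycle 2. A site following Section 8.2.3 literally could let a child leave after the end-of-infusion vital signs and PK sample on the first day of durvalumab and of the combination. It would then have to keep the same child for an hour one cycle later.

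What is at stake is how quickly a reaction soon after first exposure is recognised and managed. Section 8.3.13 says that "infusion-related reactions and hypersensitivity/anaphylactic reactions with a different underlying pharmacological etiology are also considered AESIs". Reporting is not at risk, because adverse events are collected until 90 days after the last dose (Section 8.3.2).

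A smaller wording point goes with this. Section 6.1.2 and Table 2 footnote p give the one-hour interval between the drugs for all combination days and do not say that it is subject to the waiver in Section 8.2.3.

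**Working it through.** The plan states no figure to reproduce for the observation period itself, so the check sets the schedules side by side and then sizes the gap.

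**First-exposure visits and post-infusion observation (Sections 6.1.1, 8 and 8.2.3)**

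| Phase | First-exposure visit | Exposure | Post-infusion hour listed? |
|---|---|---|---|
| Dose-finding | Cycle 1 Day 1 | First durvalumab | Yes |
| Dose-finding | Cycle 2 Day 1 | First tremelimumab and first combination | Yes |
| Dose-expansion | Cycle 1 Day 1 | First durvalumab, tremelimumab and combination | No |

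Coverage is 2 of 2 first-exposure visits in dose-finding and 0 of 1 in dose-expansion.

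**Does another rule supply the hour?**

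- The hour between the drugs on Cycle 1 Day 1 follows tremelimumab, not durvalumab.
- The full vital signs that day stop at the end of infusion.
- The instruction to monitor after infusion by institutional standard is placed under Cycle 2 onwards, so as written it does not reach Cycle 1 Day 1.
- Section 6.1.2 gives no post-infusion period and points back to Section 8.2.3.

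**Is it consistent with the rest of the dose-expansion list?** The other two entries are strictest at Cycle 1 Day 1 and relax from Cycle 2. Only the post-infusion line points to Cycle 2. The version history suggests a reason: dose-expansion tremelimumab was once given at Cycles 2 to 5, and version 3.0 moved the combination to Cycle 1. That explanation is an inference; the mismatch in the current text is not.

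**Size in time**

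- Dose-finding, after the first durvalumab dose: 60 minutes.
- Dose-expansion, last timed step in the visible text after the first durvalumab dose: at most 10 minutes (PK sample).
- Difference: 60 − 10 = at least 50 minutes.

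Infusion times widen the contrast. Section 6.1.2 gives durvalumab over 120 minutes in Cycles 1 and 2 of dose-finding, but over 60 minutes throughout dose-expansion. From the start of the first durvalumab infusion to the last specified step:

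- Dose-finding: 120 + 60 = 180 minutes.
- Dose-expansion: 60 + at most 10 = at most 70 minutes.

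**Size in patients**

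- Evaluable: 11 + 10 = 21 if the SARCOMA cohort stops at stage 1; 26 + 10 = 36 if it completes stage 2.
- Dosed: 21 × 1.2 = 25.2 and 36 × 1.2 = 43.2.

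This reproduces Section 9.2: "the total number of patients dosed in the dose-expansion phase may range from approximately 25 to 43". The Synopsis still gives a larger range, 46 to 80. I use Section 9.2 because it follows from the current cohort sizes and matches SAP Section 1.3.

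**Clinic time for the fix**

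- Hour moved from Cycle 2 Day 1 to Cycle 1 Day 1: 0 hours net.
- Both kept: 1 hour × 25 to 43 patients = 25 to 43 hours over the phase.

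**The case against.** The strongest reply is that the gap is narrow and the harm conjectural. After the first tremelimumab infusion the child stays for the one-hour interval and then a 60-minute durvalumab infusion with three sets of vital signs, about two hours in clinic. Only the hour after durvalumab is missing. Nothing in the protocol authorises discharge at the end of infusion. Infusion reactions are also covered by the interruption and slower-restart rule in Section 6.1.2, and by toxicity guidelines in an annex that is not available here. Dose-expansion opens only after four cycles of safety data and is deliberately lighter, so dose-finding need not be the benchmark.

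Much of this limits the size of the point, and I accept it. A blood draw is not monitoring. Some Table 2 rows are redacted, so the 50 minutes compares specified steps in the visible text and does not measure unobserved time. The documents give no rate of reactions after durvalumab ends, so the clinical effect cannot be quantified. The 25 to 43 is the planned total, and enrollment status is not stated, so an amendment may reach fewer patients.

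None of it explains the line. A lighter schedule could justify dropping the hour. It does not justify skipping it at first exposure and requiring it at the second, when the other checks are relaxed. The objection to the secondary wording point is largely right: Section 6.1.2 already refers to Section 8.2.3, so that point would not stand alone.

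**Conclusion.** The concern holds. Section 8.2.3 places the dose-expansion post-infusion hour at the wrong visit, and no visible text supplies an observation period after the first durvalumab infusion. Each dosed dose-expansion patient is affected once, at first exposure: about 25 to 43 as planned. The specified follow-up after that infusion is at least 50 minutes shorter than in dose-finding.

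This rests on two assumptions: that the redacted Table 2 rows contain no observation period, which is reasonable because Section 8.2.3 is the named source, and that sites apply the section as written. Good local practice may fill the gap, but the protocol does not require it. The line should be corrected as a safety-monitoring matter. It has no bearing on endpoints, sample size or error rates.

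**What to change.** In the dose-expansion observation list of Section 8.2.3, change the visit on the post-infusion line from Cycle 2 Day 1 to Cycle 1 Day 1, leaving the one hour after both infusions as it stands. Keeping the Cycle 2 Day 1 hour as well is optional.

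In the same amendment, it would help to add to Section 6.1.2 and Table 2 footnote p that, in dose-expansion, the interval between the drugs may be waived from Cycle 2 if there was no infusion reaction, as Section 8.2.3 provides. This is a secondary clarification.

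The cost is protocol wording. Moving the hour adds no net clinic time; keeping both adds one hour per patient.
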